Name: _____
Please print

Title: _____

Signature _____

Date: _____

Address: _____

SPONSOR SIGNATURE

Study Title: A Phase 2 Randomized, Double-Blind, Placebo-Controlled Study of ATR-101 for the Treatment of Cushing's Syndrome

SPONSOR SIGNATURE

I have read and approve the protocol and appendices. My signature, in conjunction with the signature of the Investigator, confirms the agreement of both parties that the clinical trial will be conducted in accordance with the protocol and all applicable laws and regulations, including, but not limited to, the International Council on Harmonisation (ICH) Guidelines for GCP, the US Code of Federal Regulations (CFR) and the ethical principles that have their origins in the Declaration of Helsinki, as well as all applicable privacy laws.

Name: [name]
Please print

Title: Chief Medical Officer

Signature: 

Date: Mar 22, 2018

Address: [name]

[name]

[name]

SYNOPSIS

Name of Sponsor/Company: Millendo Therapeutics, Inc.	
Name of Investigational Product: ATR-101	
Title of Study: A Phase 2 Randomized, Double-Blind, Placebo-Controlled Study of ATR-101 for the Treatment of Cushing's Syndrome	
Study Center(s): Approximately 14 sites in the United States and the United Kingdom	
Studied Period: Estimated date first subject enrolled: October 2016 Estimated date last subject completed: December 2021	Phase of Development: 2
Objectives: Primary: 
To evaluate the efficacy and safety of orally-administered ATR-101 in adults with endogenous Cushing's syndrome Secondary: 
To evaluate the changes in adrenal steroids and adrenal steroid intermediatesTo evaluate the change in adrenocorticotropic hormone (ACTH)To evaluate the change in metabolic syndrome-related parameters, including fasting glucose, insulin, lipid panel, blood pressure and body mass index (BMI)To assess the safety and tolerability of ATR-101To determine the pharmacokinetics (PK) of ATR-101 and its major metabolitesTo evaluate the PK/pharmacodynamic (PD) relationships of ATR-101	
Methodology: This Phase 2 multicenter study consists of two parts: an open-label intra-subject dose-escalation period of 8 weeks' duration, followed either by a double-blind randomized withdrawal period of 4 weeks' duration (if the subject meets randomization criteria) or by an additional open label dosing period of 4 weeks' duration (if the subject does not meet randomization criteria). A study schematic is shown in Figures 1, 2, and 3 below. A detailed schedule of study assessments is presented in Appendix 1 .	
Figure 1: Study Schematic, Screening and Open-Label Dose-Escalation Periods 
The diagram illustrates the study timeline. It begins with a box labeled 'Adults with Endogenous Cushing's Syndrome' leading to a sequence of three boxes representing dose escalation: '250 mg BID', '500 mg BID', and '1000 mg BID'. This is followed by a horizontal timeline with vertical markers for 'S1 Screening' (at the start), 'T1 Enrollment' (at the end of the dose escalation), 'T2 Day 15' (midpoint of the dose escalation), 'T3 Day 29' (end of the dose escalation), 'Telephone Visit Day 43 Assess meds and AEs' (4 weeks after T3), and 'R1/A1 Day 57 Randomization into double blind withdrawal period or enrollment into additional open label period' (4 weeks after the telephone visit). The timeline is divided into 'Screening Up to 8 Weeks', 'Weeks 1-2', 'Weeks 3-4', 'Weeks 5-6', 'Weeks 7-8', and the 'Open-Label Dose Escalation' period between T1 and T2.
	

Figure 2: Study Schematic, Double-Blind Randomized Withdrawal Period

[figure not shown]
[figure not shown]

Figure 3: Study Schematic, Additional Open-Label Dosing Period

During a screening period of up to 8 weeks' duration, subjects will undergo a wash-out of medications used to treat Cushing's syndrome (if needed) and will then perform two 24-hour (hr) urine collections for baseline urinary free cortisol (UFC) assessment within 28 days prior to enrollment into the open-label dose-escalation period. At enrollment, all eligible subjects will be assigned to one of two 24-hr UFC strata. Strata will be assigned according to baseline 24-hr UFC values, calculated as the mean of all 24-hr UFC levels obtained within the 28 days prior to enrollment:

- Stratum I: 24-hr UFC 1.3 to < 4 × upper limit of normal (ULN)
- Stratum II: 24-hr UFC 4 to 10 × ULN

Enrollment into a particular stratum may be limited to ensure the inclusion of subjects in both strata.

Open-Label Dose-Escalation Period: The open-label dose-escalation period will be 8 weeks in duration and will allow each subject to receive three dose levels of ATR-101 (i.e., 250 mg twice daily (BID), 500 mg BID,

and 1000 mg BID). The 250 mg and 500 mg BID dose levels will each be used for 2 weeks, and the 1000 mg BID dose level will be used for 4 weeks.

- Study Days 1-14: At Visit T1, all subjects will be assigned to take the same starting dose of ATR-101, 250 mg BID, at the beginning of the open-label dose-escalation period. Twenty-four-hour UFCs will be assessed on Days 13 and 14 (collections start on Days 13 and 14, respectively, and finish on Days 14 and 15, respectively).
- Study Days 15-28: At Visit T2, all subjects will be assigned to take the next higher dose of ATR-101, 500 mg BID. Twenty-four-hour UFCs will be assessed on Days 27 and 28 (collections start on Days 27 and 28, respectively, and finish on Days 28 and 29, respectively).
- Study Days 29-56: At Visit T3, all subjects will be assigned to take the next higher dose of ATR-101, 1000 mg BID. Twenty-four-hour UFCs will be assessed on Days 41, 42, 50, 51, and 56 (collections start on Days 41, 42, 50, 51, and 56, respectively, and finish on Days 42, 43, 51, 52, and 57, respectively).

At any time, the ATR-101 dose may be down-titrated as needed for safety reasons at the discretion of the Investigator. There will be no wash-out period between the open-label dose-escalation period and either the double-blind randomized withdrawal period or the additional open-label dosing period.

Double-blind Randomized Withdrawal Period: The double-blind randomized withdrawal period will be up to 4 weeks in duration. A subject is eligible to enter the double-blind randomized withdrawal period if the mean of the Day 50 and Day 51 (“mean Day 50/51”) 24-hr UFCs meets at least one of the following randomization criteria:

- 24-hr UFC \leq ULN
- 24-hr UFC \leq 50% relative to the baseline value

Eligible subjects will be randomized in a 1:1 ratio to receive either ATR-101 at the same dose level on which they achieved the mean Day 50/51 24-hr UFC \leq ULN (or \leq 50% of their baseline value) or matching placebo. Subjects will continue in the double-blind randomized withdrawal period for 4 weeks or until their mean Day 64/65 24-hr UFC is $> 1.3 \times$ ULN and has also increased by $> 50\%$ relative to their mean Day 50/51 24-hr UFC, whichever comes first. Subjects who are not eligible to be randomized will enter the Additional Open-Label Dosing Period instead of the Double Blind Randomized Withdrawal Period (see below).

- Study Days 57-70: Twenty-four-hour UFCs will be collected on Days 64 and 65 (collections start on Days 64 and 65, respectively, and finish on Days 65 and 66, respectively). At the time of Visit R2 (Day 71), if the mean Day 64/65 24-hr UFC result is available and is $> 1.3 \times$ ULN, and has also increased by $> 50\%$ relative to the mean Day 50/51 24-hr UFC, the subject will complete the End-of-Treatment (EoT) visit (Visit R3) instead of Visit R2 and may then be started on another agent at the discretion of his or her physician. Otherwise, the subject will continue in the double-blind, randomized withdrawal period.
- Study Days 71-85: Twenty-four-hour UFCs will be collected on Days 79 and 84 (collections start on Days 79 and 84, respectively, and finish on Days 80 and 85, respectively). The EoT visit (Visit R3) will be completed on Day 85. Note: if the mean Day 64/65 24-hr UFC was not available at the time of Visit R2, but subsequently is found to meet criteria for study completion, the EoT visit should be performed as soon as practicable, rather than on Day 85. Additionally, if the Day 79 or Day 84 24-hr UFC is $>$ ULN, after completion of the EoT visit (Visit R3) the subject may begin treatment with another agent at the discretion of his or her physician.

Additional Open-Label Dosing Period: The additional open-label dosing period will be 4 weeks in duration. A subject is eligible to enter the additional open-label dosing period if they do not meet any of the randomization criteria described in the above section.

Eligible subjects will be assigned to take ATR-101 1000 mg BID (or a lower dose if needed for safety, at the discretion of the Investigator). Subjects will continue in the additional open-label dosing period for 4 weeks.

- Study Days 57-70: Twenty-four-hour UFCs will be collected on Days 69 and 70 (collections start on Days 69 and 70, and finish on Days 70 and 71, respectively).

- **Study Days 71-85:** Twenty-four-hour UFCs will be collected on Days 79 and 84 (collections start on Days 79 and 84, respectively, and finish on Days 80 and 85, respectively). The EoT visit (Visit A3) will be completed on Day 85. Note: if the Day 79 or Day 84 24-hr UFC is > ULN, after completion of the EoT visit (Visit A3) the subject may begin treatment with another agent at the discretion of his or her physician.

Follow-up Period: During the follow-up period, subjects will continue to be monitored for safety. Subjects whose most recent 24-hr UFC is \leq ULN will have a follow-up visit (Visit F1) at the study site 2 weeks after their ET/EoT visit. Subjects whose most recent 24-hr UFC is $>$ ULN will have a follow-up telephone visit instead of a study site visit.

- **Study Days 86-98:** If the Day 79 24-hr UFC is \leq ULN, a follow-up visit (Visit F1) at the study site will be scheduled for Day 98, 2 weeks after the EoT visit. This visit will consist largely of safety assessments. Subjects whose Day 84 24-hr UFC is also \leq ULN will begin a 24-hr urine collection on Day 92 and finish on Day 93. If the Day 79, Day 84 or Day 92 24-hr UFC is $>$ ULN, a telephone visit will be conducted on Day 98 instead of a study site visit (in case of discrepant results, the latest result should be used). If the Day 92 24-hr UFC result is unknown at the time the Day 98 visit is due, the subject will proceed with having the Day 98 visit at the study site.
- **Subjects whose Day 92 24-hr UFC is \leq ULN should continue to be followed up and have morning serum ACTH and 24-hr UFC assessed every 2-4 weeks until their 24-hr UFC is $>$ ULN or until the Investigator and the Medical Monitor agree that the subject is stable.**

Throughout the course of the study, safety evaluations will include assessment of AEs, concomitant medications, clinical laboratory tests, vital signs, physical examinations (PEs) and 12-lead electrocardiograms (ECGs).

It is anticipated that the overall duration of the study per subject will range from approximately 16-22 weeks, depending upon the duration (if any) required for wash-out and the duration of follow-up.

Number of Subjects (planned): Approximately 16 adults with endogenous Cushing's syndrome

Diagnosis and Criteria for Inclusion:

Inclusion Criteria:

Each subject must meet all of the following criteria to be enrolled in this study:

1. Provision of signed and dated informed consent prior to any study-specific procedures
2. Men and women 18-80 years of age (inclusive) at screening
3. Subjects must have a confirmed diagnosis of endogenous Cushing's syndrome as evidenced by baseline UFC 1.3 to 10 \times ULN (mean of all 24-hr UFC levels obtained during the screening period within 28 days of enrollment into the open-label dose-escalation period) AND documentation at any time of ONE of the following three criteria:
 - For subjects with a diagnosis of pituitary Cushing's syndrome, either:
 - Magnetic resonance imaging (MRI) confirmation of pituitary adenoma (greater than or equal to 0.6 cm), OR
 - For subjects with a pituitary microadenoma less than 0.6 cm, bilateral inferior petrosal sinus sampling (BIPSS) showing an ACTH gradient $>$ 2 before or $>$ 3 after corticotropin-releasing hormone (CRH) or desmopressin (DDAVP) stimulation, OR
 - For subjects who have had prior pituitary surgery: histopathology confirming an ACTH-staining adenoma
 - For subjects with a diagnosis of adrenal Cushing's syndrome: MRI or computed tomography (CT) of the adrenal glands showing an adrenal tumor
 - For subjects with a diagnosis of ectopic ACTH as the cause of their Cushing's syndrome: ACTH-dependent Cushing's syndrome and either:
 - MRI showing no pituitary adenoma, OR
 - MRI showing only a small pituitary adenoma ($<$ 0.6 cm) AND a negative BIPSS, OR
 - For subjects who have had prior pituitary surgery: histopathology that is negative for an ACTH-staining adenoma

4. Subjects with a history of prior pituitary surgery must be at least 3 months post-surgery at the time of the screening visit
5. Body mass index (BMI) between 18 and 60 kg/m², inclusive, at screening
6. Female subjects must be postmenopausal > 2 years OR must have been permanently surgically sterilized (bilateral salpingectomy or tubal occlusion) > 2 years OR male partner(s) has had a vasectomy > 2 years OR must consent to use two permitted medically-acceptable methods of contraception throughout the study during any sexual intercourse with a male partner. Permitted medically-acceptable methods of birth control for this study include oral contraceptives, contraceptive implants, Depo-Provera®, contraceptive patch, vaginal ring, male condom, female condom, spermicide, diaphragm with spermicide, cervical cap with spermicide, contraceptive sponge, or an intrauterine device (IUD); IUDs must have been in place for at least 28 days prior to first dose of study drug.

Exclusion Criteria:

Subjects who meet any of the following criteria will be excluded from participation in the study:

1. Pseudo-Cushing's syndrome, cyclic Cushing's syndrome or current iatrogenic Cushing's syndrome
2. Subjects who are considered candidates for surgical treatment of Cushing's syndrome, unless it is clearly documented that the subject has refused such surgery or that surgery cannot be scheduled for at least the anticipated duration of the study
3. Normal late night salivary cortisol value during screening, unless the subject's history clearly demonstrates that he or she does not have pseudo-Cushing's or cyclic Cushing's. If the subject has a normal late night salivary cortisol, and the PI feels the subject does not have pseudo-Cushing's or cyclic Cushing's, the subject may be enrolled with approval of the medical monitor
4. Normal 24-hr UFC during screening (this would be suggestive of cyclic Cushing's)
5. Radiotherapy of the pituitary within 6 months prior to or during screening
6. For subjects with pituitary Cushing's syndrome, any compression of the optic chiasm or the presence of a tumor within 2 mm of the optic chiasm on the most recent pituitary MRI prior to or during screening
7. Use of or medical requirement for any of the following medications within the timeframes specified below prior to collection of the first 24-hr UFC during Screening and throughout study participation (see Section 5.11 for additional prohibited and restricted medications):
 - Inhibitors of steroidogenesis (ketoconazole, metyrapone): 1 week
 - Pituitary-directed agents: Dopamine agonists (bromocriptine, cabergoline) and PPAR γ agonists (rosiglitazone or pioglitazone): 4 weeks
 - Octreotide LAR, Lanreotide SR and Lanreotide autogel: 14 weeks
 - Octreotide (immediate release formulation): 1 week
 - Pasireotide: 4 weeks
 - Mitotane: 26 weeks
 - Mifepristone: 3 weeks
8. Uncontrolled diabetes mellitus, as evidenced by HbA1c > 9.0% at screening
9. Uncontrolled hypertension, defined as systolic blood pressure > 160 mmHg or diastolic blood pressure > 90 mmHg during screening. Note: if appropriate, subjects may have blood pressure medications adjusted and blood pressure reassessed at an unscheduled visit prior to Visit T1.
10. Any history of gastric or small intestinal surgery or any current disease that causes malabsorption. Note: irritable bowel syndrome is acceptable for inclusion
11. Alcohol or substance abuse (cocaine, amphetamines and/or opioids) within the year prior to screening
12. Abnormal laboratory values as per the guidelines listed below or any other clinically significant, unexplained laboratory abnormality according to the Investigator:
 - Serum ALT or AST > 3 \times ULN
 - Serum total bilirubin > 1.5 \times ULN
 - Serum creatinine > 1.5 \times ULN
 - Glomerular filtration rate < 60 mL/min/1.73 m²
13. Pregnant, breast-feeding, having conceived within the 6 months prior to screening, or having an intent to become pregnant during the study period
14. QTc > 470 msec on electrocardiogram at screening (subjects with a single QTc > 470 msec may have 2 additional ECGs taken during screening and the QTcs averaged; if the average QTc is > 470 msec then the subject is excluded)
15. Known history of Gilbert's syndrome

16. HIV, hepatitis B, or hepatitis C positivity at screening
17. Any malignancy within the previous 5 years, other than curatively treated basal or squamous cell skin cancer or cervical carcinoma *in situ*
18. Previous exposure to any amount of ATR-101
19. Participation in any study of an investigational drug within 30 days prior to screening
20. Significant psychiatric disease, recent severe physical stress, malnutrition, chronic excessive exercise, or any other medical or psychiatric condition that, in the opinion of the Investigator, is likely to confound the interpretation of the study results or prevent the subject from understanding the requirements of or successfully completing the study

Investigational Product, Dosage and Mode of Administration:

ATR-101 250-mg and 500-mg tablets for oral administration, one tablet twice per day for the 250 mg and 500 mg BID doses, respectively; and two 500-mg tablets twice per day for the 1000 mg BID dose

Duration of Treatment:

8 weeks in the open-label dose-escalation period and up to 4 weeks in the double-blind randomized withdrawal period or the additional open-label period

Reference Therapy, Dosage and Mode of Administration:

Placebo matching tablets for the ATR-101 500-mg tablets during the double-blind randomized withdrawal period

Study Endpoints:

Primary Efficacy Endpoint:

- The proportion of subjects with either a normal 24-hr UFC or a reduction in 24-hr UFC of $\geq 50\%$ relative to their baseline value at the end of the double-blind randomized withdrawal period

Secondary Efficacy Endpoints: The secondary efficacy endpoints will include the following. Unless otherwise specified in the Statistical Analysis Plan, the endpoints will be evaluated for each post-baseline visit, at the end of the open-label dose-escalation period and at the end of the double-blind randomized withdrawal period, for the ITT population as a whole and for each baseline UFC stratum.

- The proportion of subjects with a normal 24-hr UFC at the end of the double-blind randomized withdrawal period
- The proportion of subjects with a reduction in 24-hr UFC of $\geq 50\%$ relative to their baseline value at the end of the double-blind randomized withdrawal period
- The proportion of subjects with a normal 24-hr UFC at the end of the open-label dose-escalation period and at the end of the additional open-label dosing period
- The proportion of subjects with a reduction in 24-hr UFC of $\geq 50\%$ relative to their baseline value at the end of the open-label dose-escalation period and at the end of the additional open-label dosing period
- The change and percentage change in the 24-hr UFC from randomization at the end of the double-blind randomized withdrawal period
- The change and percentage change in the 24-hr UFC from baseline at the end of the open-label dose-escalation period and at the end of the additional open-label dosing period
- The proportion of subjects with a normal late night salivary cortisol at the end of the double-blind randomized withdrawal period
- The proportion of subjects with a normal late night salivary cortisol at the end of the open-label dose-escalation period and at the end of the additional open-label dosing period
- The change and percentage change in the late night salivary cortisol from randomization at the end of the double-blind randomized withdrawal period
- The change and percentage change in the late night salivary cortisol from baseline at the end of the open-label dose-escalation period and at the end of the additional open-label dosing period
- The change and percentage change from baseline in blood hormone levels, including 11-DOC, 17-OHP, A, A4, ACTH, cortisol, DHEA, DHEAS, free T, P, renin, SHBG and total T

- The change from baseline in fasting glucose, insulin, lipid panel, systolic blood pressure, diastolic blood pressure and BMI

Pharmacokinetic Endpoints:

- The C_{max} , T_{max} , AUC, $t_{1/2}$ and other PK parameters of ATR-101 and its major metabolites (as appropriate and as the data allow)
- The relationship between C_{max} and AUC vs. the percentage change in 24-hr UFC; other PK/PD relationships may be explored as appropriate and as data allow

Safety Endpoints: Safety endpoints will include the incidence of treatment-emergent adverse events and serious adverse events, as well as changes from baseline in PEs, safety laboratory tests and ECG parameters.

Statistical Methods:

A Statistical Analysis Plan that includes a more technical and detailed description of the planned statistical analyses will be prepared prior to unblinding of the double-blind randomized withdrawal period of the study.

Analysis Populations:

Efficacy – The primary efficacy analysis population will be the Intent-to-Treat (ITT) population, based on all subjects who are randomized into the double-blind randomized withdrawal period and take at least one dose of double-blind study drug. The modified ITT (mITT) population, based on all subjects who complete at least 2 weeks in the double-blind randomized withdrawal period of the study, will be used for additional analyses. For efficacy analyses, subjects will be included in the treatment group to which they were randomized.

Safety – The safety population will include all treated subjects. Safety analyses will be based on the safety population. For the safety analyses for the double-blind randomized withdrawal period, subjects randomized to the placebo group who receive ATR-101 will be included in the treatment group of the active study drug that they received.

Pharmacokinetic – The PK population will include all subjects with measurable drug concentrations. PK analyses will be based on the PK population.

Sample Size:

A sample size of 16 enrolled patients is sufficient per clinical considerations. No formal sample size calculation was performed.

Analysis Methodology:

Primary endpoint – The primary efficacy endpoint, the proportion of subjects with either a normal 24-hr UFC or a reduction in UFC of $\geq 50\%$ relative to their baseline value at the end of the double-blind randomized withdrawal period, will be evaluated using the Cochran-Mantel-Haenszel (CMH) test, controlling for baseline 24-hr UFC stratum.

Secondary endpoints – No further adjustments for multiple group comparisons, multiple additional endpoints or multiple subgroups of interest are planned.

Responder analyses and other categorical analyses will be based on the CMH test or Fisher's exact test, as appropriate and if the data allow. Continuous endpoints will be evaluated using ANCOVA or ANOVA model methodology, as appropriate and if the data allow.

Exploratory endpoints – Additional efficacy endpoints may be pre-specified in the Statistical Analysis Plan, including sensitivity analyses associated with drug compliance and missing data issues.

Safety endpoints – Adverse events counts (overall, as well as by severity, causality and seriousness) will be tabulated by Medical Dictionary for Regulatory Activities (MedDRA) system organ class and preferred term. Descriptive statistics and shift tables will be used to summarize continuous laboratory, blood pressure and ECG parameters. Counts and shift tables will be used for categorical lab parameters.

Pharmacokinetic endpoints – PK assessments will be performed at each dose level to determine ATR-101 exposures and to profile PK/PD relationships. PK assessments will include C_{max} , AUC_{0-4} and trough levels.

Individual subject PK data will be analyzed along with pooling of subjects' data at each dose level. Individual PK parameters will be derived using the WinNonlin software, and table summaries will be provided using descriptive summary statistics.

TABLE OF CONTENTS

SYNOPSIS	4
TABLE OF CONTENTS.....	11
LIST OF TABLES.....	16
LIST OF FIGURES	16
LIST OF ABBREVIATIONS.....	17
1. INTRODUCTION	20
1.1. Background.....	20
1.2. Rationale for the Use of ATR-101 in Cushing's Syndrome.....	20
1.2.1. Preclinical Studies	21
1.2.2. Clinical Studies.....	22
1.3. Research Hypothesis.....	22
1.4. Rationale for Conducting This Study	22
2. STUDY OBJECTIVES	23
2.1. Primary Objective.....	23
2.2. Secondary Objectives	23
3. INVESTIGATIONAL PLAN.....	24

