3.1.5. Follow-up Period

During the follow-up period, subjects will continue to be monitored for safety. Subjects whose most recent 24-hr UFC is \leq ULN will have a follow-up visit (Visit F1/End-of-Study, EoS; this is the same as the end of trial) at the study site 2 weeks after their ET/EoT visit. Subjects whose most recent 24-hr UFC is $>$ ULN will have a follow-up telephone visit instead of a study site visit.

- Study Days 86-98: If the Day 79 24-hr UFC is \leq ULN, a follow-up visit (Visit F1) at the study site will be scheduled for Day 98, 2 weeks after the EoT visit. This visit will consist largely of safety assessments. Subjects whose Day 84 24-hr UFC is also \leq ULN will begin a 24-hr urine collection on Day 92 and finish on Day 93. If the Day 79, Day 84 or Day 92 24-hr UFC is $>$ ULN, a telephone visit will be conducted on Day 98 instead of a study site visit (in case of discrepant results, the latest result should be used). If the Day 92 24-hr UFC result is unknown at the time the Day 98 visit is due, the subject will proceed with having the Day 98 visit at the study site.
- Subjects whose Day 92 24-hr UFC is \leq ULN should continue to be followed up and have morning serum ACTH and 24-hr UFC assessed every 2-4 weeks until their 24-hr UFC is $>$ ULN or until the Investigator and the Medical Monitor agree that the subject is stable.

Throughout the course of the study, safety evaluations will include assessment of AEs, concomitant medications, clinical laboratory tests, vital signs, physical examinations (PEs) and 12-lead electrocardiograms (ECGs).

A detailed schedule of study assessments is presented in [Appendix 1](#).

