6.9.5. Pregnancy Reporting

Any pregnancy following study drug dosing where the estimated date of conception occurred either prior to the study termination visit or within 30 days of last study treatment must be reported. The Investigator should report the pregnancy to Medpace Clinical Safety within 24 hrs of being notified. Medpace Clinical Safety will then forward the Exposure *In Utero* form to the Investigator for completion. **The contact information for reporting pregnancies is the same as for reporting SAEs (Section 6.9.4.2).**

A subject becoming pregnant while on study drug will immediately be withdrawn from the study and early termination study procedures will be performed.

The subject should be followed by the Investigator until completion of the pregnancy. If the pregnancy ends for any reason before the anticipated date, the Investigator should notify Medpace Clinical Safety. At the completion of the pregnancy, the Investigator will document the outcome of the pregnancy. If the fetus has a congenital anomaly, the Investigator should follow the procedures for reporting an SAE.

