7. STUDY ACTIVITIES

During the study, blood samples for hormones should be collected between 6-10 AM (06:00-10:00), as close to 8 AM (08:00) as practicable. Early morning saliva samples should be collected 30-45 minutes after awakening for the day. Late night saliva samples should be collected between 10 PM and 12 AM (22:00-00:00). Within this protocol, references to the study day of a 24-hr UFC collection mean that the collection was to have begun on that study day (e.g., a “Day 14” 24-hr UFC is one that was to have begun on Day 14 and completed on Day 15). All sample collections and study visits and procedures from Visit T1 to Visit R3/A3/ET have a window of + 2 days. All other sample collections, study visits, and procedures have a window of ± 7 days.

Study visit designations (S1, T1, etc.) are shown in the detailed schedule of study assessments presented in [Appendix 1](#).

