7.4. Additional Open-Label Dosing Period

Subjects whose mean Day 50/51 24-hr UFC level does NOT meet randomization criteria (i.e., it is NOT either \leq ULN or \leq 50% of their baseline value) are eligible to enter the 4-week additional open-label dosing period. (Subjects who DO meet either of these randomization criteria will instead enter the 4-week double-blind randomized withdrawal period, described in Section 7.3.) Subjects entering the additional open-label dosing period will be assigned to take ATR-101 1000 mg BID. Subjects' 24-hr UFC levels will be followed during this period to determine the efficacy of a longer duration of dosing with ATR-101 in achieving lowered levels.

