7.5.2. Follow-up, Visit F1 (End-of-Study (EoS); End of Trial)

The target study day for the follow-up (EoS; end-of-trial) visit is 13 days after Visit R3/A3/ET. Only subjects whose most recent available 24-hr UFC is \leq ULN need to have a follow-up visit at the study site. All other subjects should be followed up via telephone to assess for new AEs and concomitant medications. Subjects who have ongoing AEs should be followed up as appropriate.

Subjects whose Day 92 24-hr UFC is \leq ULN should continue to be followed up and have morning serum ACTH and 24-hr UFC assessed every 2-4 weeks until their 24-hr UFC is $>$ ULN or until the Investigator and the Medical Monitor agree that the subject is stable.

At Visit F1 (EoS; end of trial), appropriate study site personnel should:

- Record adverse events and update medications.
- Record vital signs and weight.
- Perform a brief PE, with particular attention to assessing the subject for adrenal insufficiency.
- Collect blood samples for hematology, chemistry and hormones (11-DOC, 17-OHP, A, A4, ACTH, cortisol, DHEA, DHEAS, free T, P, renin, SHBG and total T).

- All blood hormone collections should be performed between 6-10 AM (06:00-10:00), as close to 8 AM (08:00) as practicable.
- Subjects need to be in a seated position for at least 15 minutes prior to collection of blood hormone levels so that renin and aldosterone levels are stable.
- If the subject is a woman of childbearing potential, collect a urine sample and perform a urine pregnancy test (preferred; or submit a serum or urine sample to a laboratory for pregnancy testing if required by your institution/IRB/EC).
- If the subject's most recent available 24-hr UFC result is \leq ULN, then:
 - Provide instructions regarding a 24-hr urine sample to be collected at home within 2-4 weeks after the previous sample.
 - Schedule the next study visit (unscheduled follow-up).
- At the completion of Visit F1 and all follow-ups, once the 24-hr UFC is $>$ ULN, discharge the subject from the study.

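### Contraception is tied to the end of the study, which for women on ATR-101 with UFC still above normal falls about 14 days after the last dose and about 16 days before the 30-day pregnancy-reporting window closes

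*Protocol*

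**What the plan says.** **Contraception.** Inclusion criterion 6, worded identically in the synopsis and Section 4.1, applies to women who are not postmenopausal, not sterilized and have no vasectomized partner. They "must consent to use two permitted medically-acceptable methods of contraception throughout the study". Exclusion criterion 13 (synopsis and Section 4.2) bars women "having an intent to become pregnant during the study period". Neither criterion is anchored to the last dose.

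**End of study.** Section 3.1.5 labels Visit F1 as End-of-Study and adds that "this is the same as the end of trial". Section 7.5.2 fixes its timing: "The target study day for the follow-up (EoS; end-of-trial) visit is 13 days after Visit R3/A3/ET". Subjects whose latest UFC is above ULN have this contact by telephone. Those with a Day 92 UFC at or below ULN stay under observation, and discharge comes "At the completion of Visit F1 and all follow-ups", once UFC exceeds ULN.

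**Last dose.** Sections 7.3.4 and 7.4.4 expect it on the evening before R3/A3. Sections 7.3.3 and 7.4.3 tell subjects to take none on the morning of that visit.

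**Pregnancy reporting.** Under Section 6.9.5, a pregnancy with an estimated conception date "either prior to the study termination visit or within 30 days of last study treatment must be reported", and an in-utero exposure form follows.

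**The concern.** The protocol treats the 30 days after the last dose as a period of interest. Conceptions in it are reportable (Section 6.9.5), and adverse events are collected through it when it outlasts the final visit (Section 6.9.1). The contraception rule alone has no post-dose limb. A woman who follows criterion 6 exactly may stop contraception while a conception would still be handled as a possible in-utero exposure.

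The women most exposed are also those followed least closely. With UFC above ULN the F1 contact is by telephone and covers adverse events and medications. The F1 pregnancy test belongs to the site visit only (Section 7.5.2 and Appendix 1), so their last scheduled test is at R3/A3, about Day 85.

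The additional open-label group shows the problem most clearly: "Subjects entering the additional open-label dosing period will be assigned to take ATR-101 1000 mg BID" (a lower dose is allowed for safety), and they enter that period because their UFC was not low enough for randomization. Subjects randomized to ATR-101 whose UFC is above ULN at the end are in the same position.

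What is at stake is a minor patient-safety matter. No endpoint or analysis depends on it.

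**Working it through.** This is calendar arithmetic.

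**Inputs**
- End-of-treatment visit R3/A3: Day 85 (Sections 3.1.3 and 3.1.4).
- Last dose: evening of Day 84 (Sections 7.3.4 and 7.4.4).
- F1: R3/A3 plus 13 days (Section 7.5.2).
- F1 window: "All other sample collections, study visits, and procedures have a window of ± 7 days" (Section 7).
- Reporting window: 30 days after last treatment (Section 6.9.5).

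**The protocol's own figure.** F1 = 85 + 13 = Day 98, as in Section 3.1.5 and Appendix 1. As a check that the study is meant to end there, 98 days is 14 weeks. Adding up to 8 weeks of screening gives 22 weeks, the upper end of the 16 to 22 weeks per subject in Section 3.3.

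**Main case: active drug to Day 84, study ends at F1**
- Contraception after last dose: 98 − 84 = 14 days.
- Reporting window closes: 84 + 30 = Day 114.
- Uncovered interval: 114 − 98 = 16 days.
- F1 seven days early (Day 91): 7 days covered, 114 − 91 = 23 uncovered.
- F1 seven days late (Day 105): 21 days covered, 114 − 105 = 9 uncovered.

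**Other paths**

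| Path | Last active dose | Study ends | 30 days reached | Uncovered |
|---|---|---|---|---|
| Active, early completion at Day 71 | Day 70 | 71 + 13 = Day 84 (77–91) | Day 100 | 16 days (9–23) |
| Active, Day 92 UFC ≤ ULN | Day 84 | no earlier than next sample, 92 + 14 = 106 to 92 + 28 = 120 | Day 114 | 0–8 days |
| Randomized to placebo | Day 56 | Day 98 (91–105) | Day 86 | none |

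The third path reads the study as lasting until discharge. In the placebo arm, F1 comes 98 − 56 = 42 days (35–49) after the last active dose, which is 12 days (5–19) beyond Day 86.

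**The case against.** The strongest reply is that the two rules serve different purposes. Criterion 6 restricts behavior, whereas Section 6.9.5 is a surveillance net that may reasonably be cast wider. A difference between them is not a contradiction and does not show harm. The protocol gives no half-life value and no reproductive-toxicity data, and the Investigator's Brochure and consent form are not at hand. The need for exactly 30 days therefore cannot be demonstrated, and the consent form may already contain a post-dose instruction. Two weeks is also a real margin for a twice-daily drug, and several permitted methods (implant, intrauterine device, injection) would not lapse on Day 98. This all stands, and it keeps the point minor.

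It does not remove the point. Nothing in the protocol argues for 14 days: the cut-off is a by-product of when F1 is scheduled. Reversibility is not a given either. Section 1.2.1 describes only partial reversal of effects in dogs, with signs of recovery in one of two females four weeks after the 13-week study. Section 3.6 says that the preclinical exposures showing adrenal changes were much higher than those expected here, so this is a reason for caution and not evidence of harm.

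One could also read the study as including the 30 days of adverse-event collection. But Section 6.9.1 names the last visit and the 30-day mark as separate end points, and Section 3.1.5 puts the end of trial at F1.

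**Conclusion.** The concern holds as a low-priority improvement. For women who received ATR-101 to the end of treatment and leave the study at F1 with UFC above ULN, the contraception requirement stops about 14 days (7–21) after the last dose. That leaves about 16 days (9–23) of the protocol's own 30-day window uncovered.

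These figures assume that the last dose is taken the evening before R3/A3, that visits other than F1 are on target, and that the study ends for these women at F1.

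The gap shrinks to 0–8 days in extended follow-up and does not concern active drug in the placebo arm. The number of women affected is not given; within about 16 enrolled subjects it will be small. Whether 30 days is the right duration depends on the Investigator's Brochure. Confidence is medium.

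**What to change.** - **Inclusion criterion 6 (synopsis and Section 4.1):** require contraception during the study *and for at least 30 days after the last dose of study drug*, or longer if the Investigator's Brochure supports it.
- **Exclusion criterion 13 (synopsis and Section 4.2):** extend the period of intended pregnancy to 30 days after the last dose, for consistency. This adds little protection, because intent is judged at entry.
- **Consent form:** align it if it differs.

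Assignment is blinded, so one rule must serve both randomized arms.

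The cost is one line of wording in each place. No visit, test or analysis is added. The burden is about two more weeks of contraception for the few women affected, including placebo subjects who do not need it on account of active drug.
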